pump, glucometer, CGM). The subject will be asked to provide downloaded data periodically during the month (approximately 3-5 times) using a web-based diabetes management system (e.g. Diasend, Carelink Pro, etc.) and local diabetes device management software (e.g. Dexcom Studio). The study team will review subject data to ensure proper data collection. Study team will review quantity and quality of the data. Additional download request may occur depending upon the quality of the data collected.

3. Subject will be advised to consistently use the bolus calculator (or “wizard”) of their insulin pump if on CSII or their carb counting parameters to calculate meal insulin if on MDI.
4. Optional: Subjects will be asked to wear a Fitbit during the data collection phase, removing prior to bathing and participating in water activities.
5. The subject may be asked to repeat up to 4 weeks of the Data Collection Period.
6. If the subject is unable to provide the downloaded data from home, the subject will be asked to return to the office so the study team can assist them.
7. The subject may return to the office at any time for additional support.
8. If a change in the basal insulin dose is recommended and accepted by the physician for an MDI user, the subject will be instructed to use the new basal dose(s) for approximately 5 days prior to the Experimental admission. The subject will be instructed to maintain a minimum of 7 SMBG per day, and the study clinical team will contact the subject within 72h of the dose change to monitor safety.
9. Visit 5 admission may be delayed no greater than 100 days.

Visit 4: Research House/Hotel Admission (Randomized)

Pre-Admission Procedures

1. The subject will insert new CGM sensor ~24-36 hours prior to the start of the research house/hotel admission.
2. Subjects will be asked to maintain their regular exercise pattern on the day prior to each research house/hotel admission.
3. The subject will meet the study team and check in to the research house/hotel at approximately 16:00-17:00.
4. The subject will be asked to perform a fingerstick using the study glucometer and ketone

meter shortly after arrival. If glucose is <80 mg/dL or >300 mg/dL or β -Ketone test is >0.6 mmol/L, the study physician will suggest appropriate treatment per the Glycemic Treatment Guidelines. The study subject may continue participation in the trial when blood glucose levels are between 80-300 mg/dL and ketone values are below 0.3 mmol/L.

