- a. **Experimental Admission** – The subject will inform DiAs of the breakfast meal carbohydrates and current blood glucose level by activating the meal screen of the system. Insulin will be administered based on the new therapy regimen (basal profile, correction factor and carbohydrate ratio profiles) and according to the subject's estimate of the carbohydrate content of the meal. The subject will self-administer the DiAs-calculated meal bolus under study staff supervisor.
- b. **Control Admission** – The subject will inform DiAs of the breakfast meal carbohydrates and current blood glucose level by activating the meal screen of the system. Insulin will be administered based on the subject's regular therapy regimen (basal profile, correction factor and carbohydrate ratio profiles) and according to the subject's estimate of the carbohydrate content of the meal. The subject will self-administer the DiAs-calculated meal bolus under study staff supervisor. The subject may use a temporary basal rate in preparation for exercise per the subject's usual routine.

4. **Exercise Session:** The subject will perform a controlled exercise activity designed to maintain (HR) at ~140 bpm and starting at approximately 11:00 AM. The exercise will consist of 45 minutes of cardiovascular activities that are divided into consecutive 15 minute periods. Fingerstick BG will be performed before and after each 15 minute exercise bout and entered into DiAs via the BG entry screen. Blood glucose value must be ≥ 80 mg/dL to initiate each 15 minute exercise bout. Immediately prior and during exercise, fingerstick BG < 100 mg/dL will be treated according to the Hypoglycemia Treatment Guidelines. Subjects will wear a heart rate monitor during this exercise session.

- a. **Experimental Admission** – The subject or study staff will inform DiAs of the impending exercise session by pressing the exercise advice button. The exercise advice given by DiAs will be followed and may consist of the following:
 - i. If no risk of hypoglycemia is detected, no intervention will be recommended.
 - ii. If a mild-moderate risk of hypoglycemia is detected, DiAs will recommend a 0% temp basal rate x 1 hour for CSII users and a 12-16 gram snack for MDI users.
 - iii. If a high risk of hypoglycemia is detected, DiAs will recommend a 0% temp basal rate x 1 hour plus a 12-16 gram snack for CSII users and a 24-32 gram snack for MDI users.

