- a. Experimental Admission – The subject will inform DiAs of the lunch meal carbohydrates and current blood glucose level by activating the meal screen of the system. Insulin will be administered based on the new therapy regimen (basal profile, correction factor and carbohydrate ratio profiles) and according to the subject's estimate of the carbohydrate content of the meal. The subject will self-administer the DiAs-calculated meal bolus under study staff supervision.
- b. Control Admission – The subject will inform DiAs of the dinner meal carbohydrates and current blood glucose level by activating the meal screen of the system. Insulin will be administered based on the subject's regular therapy regimen (basal profile, correction factor and carbohydrate ratio profiles) and according to the subject's estimate of the carbohydrate content of the meal. The subject will self-administer the DiAs-calculated meal bolus under study staff supervision.

6. Quiet activities will be conducted during the afternoon and evening hours.

G. Procedures Related to Discharge

1. At approximately 16:00, DiAs will be stopped and study equipment will be removed.
2. The subject will resume his/her normal home CSII or MDI insulin therapy.
3. The subject will be discharged if the fingerstick value is 80-300 mg/dL and ketone <0.6 mmol/L. Staff will also review to ensure that the glucose trend is stable.
4. If the subject's glucose is out of the specified parameters, the Glycemic Treatment Guidelines (Appendix A-6) will be followed until the subject is in the specified range.
5. The subject will be offered a meal prior to discharge.
6. Subjects will be asked to check BG before dinner, at bedtime, and upon awakening the following day and to monitor for possible symptoms of hypoglycemia since discharge.
7. Study staff will contact the subject within 24-48 hours after discharge to enquire about AEs or BG <50 or >400 mg/dL.
8. If the first admission was the Control admission, the subject will participate in Visit 3 approximately 30 days prior to the Experimental admission. Appropriate study supplies will be provided.

Meals

1. Distribution of meals will be determined by the parameters defined by the subject's weight (Rounded to the nearest 10 kgs.) and multiplied by the carbohydrate/fat/protein ratio as described in Figure 2. Meals will be a wide variety of carbohydrate/fat/protein to fully test the optimization capabilities of the bolus calculator.

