2. Meals will be replicated during each admission.
3. The subject or study staff will enter the amount of carbohydrates into the DiAs meal screen for each meal. Carbohydrate amounts may be underestimated prior to exercise if that is the usual home routine.
4. Snacks will only be permitted if advised by DiAs prior to exercise and per the usual routine prior to bedtime. Snacking between meals will not be permitted.

Meal	Carb	Fat	Protein	Carb (g/kg)	Fat (g/kg)	Protein (g/kg)
Day 1						
Dinner	High	Low	Moderate	1	0.2	0.27
Day 2						
Breakfast	Low	Low	Moderate	0.5	0.14	0.27
Lunch	Moderate	High	Moderate	0.75	0.46	0.27
Dinner	High	High	Moderate	1	0.53	0.27
Day 3						
Breakfast	Low	Low	Moderate	0.5	0.14	0.27
Lunch	Moderate	Low	Moderate	0.75	0.17	0.27

Figure 2: Meal Composition

Equipment Specifications

1. All study equipment including the DiAs cell phone, computers, insulin pump (for CSII subjects), and CGM receivers will be set to the same time using an atomic clock as a reference.
2. The study team will train the subject on the DiAs interface until all questions are answered. However, study staff will supervise all interactions with the DiAs, including entering information for meal dosing, FSBG results, hypoglycemia treatments and temporary basal

rates.

3. The CGM tracing will be blinded on the DiAs and on the CGM receiver.
4. Subjects will wear a heart rate monitor during each exercise session.

Blood Glucose Measurements

- The subject will be instructed that all fingersticks should be preceded by hand washing with warm water and a dry towel. The subject will be instructed to obtain fingerstick, avoiding alternative sites, when obtaining blood values. The first drop of blood will be discarded. The second hanging drop will be used to measure the glucose level.
- The subject will be reminded that all treatment decisions should be based on fingerstick values and not on CGM values.
- Once a fingerstick is obtained for any reason during the admissions, the Glycemic Treatment Guidelines (Appendix A-6) will be followed to determine timing of subsequent fingersticks.
- Scheduled times: prior to meals and snacks, before and after each 15 minute exercise bout, and at bedtime (23:00).
- Prior to calibration of CGM and/or if calibration is requested by CGM.
- The subject may request any additional fingersticks as desired.

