- Study personnel may also request additional fingersticks at their discretion.
- BG treatments will be based on Glycemic Treatment Guidelines (Appendix A-6) although hypoglycemic treatments can occur at any time per the subject's request.
- If CGM <80 mg/dL, SMBG will be performed every 15 minutes. If SMBG <100 mg/dL, the Glycemic Treatment Guidelines (Appendix A-6) will be applied.
- If CGM >300 mg/dL, SMBG will be performed every 60 minutes. If SMBG >300 mg/dL, the Glycemic Treatment Guidelines (Appendix A-6) will be applied.
- In case of remote monitoring unavailability or in case of CGM failure (an alert will sound on the DiAs and on the remote monitoring), SMBG will be collected at bedtime, 3am and 7am until the issue is resolved.
- Calibrations of the CGM will be per manufacturer guidelines. Hypoglycemia treatment (e.g. glucose tablets, glucose gel/liquid, and a glucagon emergency kit) will be available for

treatment at all times.

- The subject will have access to ad lib glucose-free beverages.
- A study MD will be available for any clinical concerns.
- The Senior DiAs Engineer with remote monitoring capability will be available if needed to view the study from another location. A DiAs trained technician will be on site for any system issues.
- The subject will be accompanied by a medically qualified staff member and a technician during the admissions.

SAFETY MONITORING / RISK ANALYSIS

- **Monitoring Procedures by Staff**

1. CGM values are updated onto DiAs every 5 minutes.
2. Study staff will be constantly monitoring the CGM and subject-entered SMBG values from the remote monitoring website and alert nursing and physician staff when the CGM is <80 or >300 mg/dL.
3. If CGM < 80 mg/dL, SMBG will be performed every 15 minutes. If SMBG >80 mg/dL, the Glycemic Treatment Guidelines (Appendix A-6) will be applied during both the Experimental and Control admissions.
4. If CGM >300 mg/dL, SMBG will be performed every 60 minutes. If SMBG >300 mg/dL, the Glycemic Treatment Guidelines (Appendix A-6) will be applied Experimental and Control Admissions.
5. The DiAs trained technician will monitor the system for the first floor of the research house/hotel during the entire admission.
6. Medical personnel and emergency supplies are on the first floor of the research house/hotel but the study staff periodically round subjects' rooms on both floors during the overnight hours.

- **Glucose Monitoring Risk:**

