Bayer CONTOUR NEXT glucometer is a FDA approved 510K Class II Medical Device (510K number K121087).

- **Hypoglycemic/Hyperglycemic Risk:**

CLINICAL PROTOCOL

The Glycemic Treatment Guidelines will be followed during Visit 4 and Visit 5. The treatment guidelines are attached in Appendix A-6.

- **Calibration of CGM Risk:**

The CGM will be calibrated using fingerstick values before meals, bedtime, and as requested by the device during both the Experimental and Control Admissions. The study team may recommend calibrations as needed.

- **Sterilization Risk:**

Study equipment cannot be sterilized in an autoclave. Cleaning instructions for study equipment provided to study the subject are provided below.

- **Device Reuse Risk:**

The Dexcom Continuous Glucose Monitors are labeled for single use only. The sensor, the component of the system that enters the skin, will be single use only. The transmitter and receiver will be reused after cleaning as described below. The transmitter is attached to the sensor but does not enter the skin and the receiver is a hand held device. The transmitter and receiver will be cleaned adhering to hospital protocol as described below. The subject will be informed that the FDA has approved these devices for single use and that by using them among multiple patients, bloodborne pathogens (i.e. Hepatitis B) may be spread through the use of multiple users.

Cleaning Procedure: Equipment that touches intact skin will be cleaned with ethyl or isopropyl alcohol (70-90%), quaternary ammonium germicidal detergent (i.e. CaviCide) or household bleach. The contact time on the surface depends on the method used to clean the equipment. CaviCide requires three minutes on the surface. Clorox Germicidal Bleach Wipes require two minutes on the equipment. The surface should remain wet (i.e. slightly damp) with the disinfectant to be considered effective though not wet enough to leave drops of liquid. Equipment will be stored in a clean zipped bag.

The study glucometers are single use devices.

The insulin pens are single use devices.

Hb1Ac Risk: The University of Virginia central labs have College of American Pathologist (CAP) and the Clinical Laboratory Improvement Amendments (CLIA) certifications. While the central lab is not NGSP certified, the calibrators for the HbA1c assay are traceable to NGSP. The equipment (Tosoh G7) is NGSP certified.

- **Misuse Risk:**

CGM Training:

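### Staff-monitoring item 3 states the low-glucose action threshold backwards (SMBG above 80 mg/dL), against the below-100 rule given for the same CGM trigger

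*Combined protocol and SAP*

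**What the plan says.** The same trigger and testing frequency (CGM below 80 mg/dL, fingerstick every 15 minutes) appear twice in the protocol, with different action conditions:

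- Blood Glucose Measurements: "If SMBG <100 mg/dL, the Glycemic Treatment Guidelines (Appendix A-6) will be applied".
- SAFETY MONITORING / RISK ANALYSIS, Monitoring Procedures by Staff, item 3: "If SMBG >80 mg/dL, the Glycemic Treatment Guidelines (Appendix A-6) will be applied during both the Experimental and Control admissions".

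The high-glucose rule is also given twice. Item 4 reads "If SMBG >300 mg/dL, the Glycemic Treatment Guidelines (Appendix A-6) will be applied Experimental and Control Admissions", and the corresponding measurement bullet uses the same limit of 300 mg/dL in the same direction.

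Blood Glucose Measurements also makes the meter reading the deciding number: "The subject will be reminded that all treatment decisions should be based on fingerstick values and not on CGM values".

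**The concern.** Item 3 is an operative instruction for staff answering a low-glucose alert in people on insulin, some of whom are about to exercise. The CGM is blinded to the subject, so staff are the ones who respond to a CGM low, and the fingerstick then decides treatment. Staff working from the monitoring section read a threshold that points the opposite way from the one in the measurement section. Taken literally, item 3 does nothing when the meter confirms the low, and acts when the meter does not support the CGM reading.

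What is at stake is a clear, uniform response to lows during the admissions. No sample size, test or other statistical figure depends on this line.

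**Working it through.** The plan gives no figure to reproduce. The check sets the two rules side by side and then compares item 3 with the protocol's other low-glucose limits.

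**1. The two rules after CGM below 80 mg/dL, in whole-number meter readings**

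| Fingerstick (mg/dL) | Measurement bullet (<100) | Item 3 as written (>80) |
|---|---|---|
| 80 or below | triggers | does not trigger |
| 81 to 99 | triggers | triggers |
| 100 or above | does not trigger | triggers |

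Both rules trigger only at 81-99: 99 − 81 + 1 = 19 values. At every other reading exactly one of them triggers.

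**2. Candidate corrections to item 3**

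- Sign only (<80): the rules differ at 80-99, which is 99 − 80 + 1 = 20 values.
- Changed to <100: the rules differ at 0 values.

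**3. Direction of every low-glucose rule with a numeric limit**

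| Place in the protocol | Text or limit | Acts |
|---|---|---|
| Visit 4, Pre-Admission Procedures, item 4 (check-in) | "If glucose is <80 mg/dL or >300 mg/dL" | below 80 |
| Day 2, Exercise Session | "Immediately prior and during exercise, fingerstick BG < 100 mg/dL will be treated according to the Hypoglycemia Treatment Guidelines" | below 100 |
| Day 3, Exercise Session | limit of 100, once exercise has begun | below 100 |
| Procedures Related to Discharge, items 3 and 4 | "The subject will be discharged if the fingerstick value is 80-300 mg/dL and ketone <0.6 mmol/L"; Guidelines followed outside the range | below 80 |
| Blood Glucose Measurements | bullet quoted above | below 100 |
| Monitoring Procedures by Staff, item 3 | quoted above | **above 80** |

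Five of the six act below their limit. Item 3 alone acts above it.

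**4. Could the sign be a PDF reading error?** This cannot be fully excluded. However, the CGM limit in the same item prints with the expected sign, as do the neighbouring items, and 80 would still disagree with 100 if the sign had been misread.

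**5. Could item 3 be a deliberate rule for CGM and meter disagreement?** That reading does not rescue it, because the item gives no instruction for a fingerstick of 80 or below.

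**Two separate, minor wording points.**

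- The Day 2 exercise rule covers the time just before exercise as well as during it. The Day 3 rule starts only once exercise is under way. Since 80 mg/dL is enough to begin a bout, a reading of 80-99 before the first bout falls under the Day 2 exercise rule but not the Day 3 one.
- Table 3 (Outpatient Emergency Plan) tells the nurse to remove a study pump. Under Day 1, CSII subjects use their home pump, and MDI subjects use pens or syringes.

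**The case against.** The strongest reply is that each line says when the Guidelines will be applied and neither forbids them otherwise. Below 100 and above 80 together cover every possible reading, so staff who follow both lines apply Appendix A-6 every time. Lows are also caught elsewhere:

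- Item 2 of the same staff list alerts nursing and physician staff at CGM below 80, whatever the fingerstick shows.
- Hypoglycemic/Hyperglycemic Risk says "The Glycemic Treatment Guidelines will be followed during Visit 4 and Visit 5".
- Blood Glucose Measurements bases glucose treatment on Appendix A-6 and allows hypoglycemia treatment at the subject's request.
- A nurse is present throughout and a physician is on call (Minimal Staffing Requirements).

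It can also be said that Appendix A-6 is not in the supplied text, so below 80 might be the intended limit. The six-rule count also includes check-in and discharge, which are different situations, and the exercise rules cite guidelines under a slightly different title.

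Much of this stands as a limit on the consequence. The value counts describe where the wording diverges; they do not count untreated events. The count of six supports the direction of the error, but only the measurement bullet shares item 3's trigger. None of this makes item 3 correct. Two lines that together trigger at every reading set no threshold, and staff working from the monitoring list alone see only the reversed one. The uncertainty about Appendix A-6 is a reason to check it before editing.

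**Conclusion.** The concern holds: item 3 gives a wrong operative safety threshold and should be corrected. It conflicts with the only other rule for the same trigger, in direction and in number, at every whole-number reading outside 81-99 mg/dL. The matching pair of high-glucose rules suggests that the two lists were meant to mirror each other.

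The consequence is limited. Other text sends glucose treatment to the Guidelines in both admissions, and item 3 is worded identically for both. The documents do not show that treatment would be withheld or that the paired comparison is biased, and any effect on LBGI cannot be determined.

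Confidence that item 3 is wrong is high. That 100 is the right limit rests on the same-trigger bullet and is subject to Appendix A-6. The Day 3 and Table 3 points are separate and do not affect this conclusion.

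**What to change.** Confirm the limit against Appendix A-6, then change item 3 to SMBG below 100 mg/dL so that it matches the measurement bullet, and brief staff. Do not reverse only the sign. The 80 mg/dL limits at check-in and discharge are gates for other situations and can stay.

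As minor separate corrections:

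- Use the Day 2 timing (just before and during exercise) in the Day 3 exercise rule.
- In Table 3, replace the study-pump step with an action for the home pump, marked as not applicable to MDI subjects. Equipment Specifications lists an insulin pump for CSII subjects among the study equipment for clock setting, so the wording there should be clarified too.

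The cost is one threshold in one line, the minor wording corrections and a staff briefing. Sample size, analysis, visits and procedures do not change.
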